7.2. Rationale for Study Design

While ARO-ENaC is intended for use in CF patients, these patients suffer from frequent disease exacerbations and are frequently on multiple concomitant medications. For this reason, this study initially evaluates each dose level in a healthy volunteer population to generate a baseline understanding of safety in a population with normal physiology and without the confounding factor of concomitant medication use.

This FIH study plans to investigate ARO-ENaC in normal healthy volunteers to evaluate the drug's safety and tolerability. The study initiates in healthy volunteers because the risk is considered low based on GLP animal toxicity testing. It is expected that treatment of CF with ARO-ENaC will require multiple doses; thus, this study in healthy volunteers transitions from a single cycle of three doses to two cycles of three doses each (on Days 1, 2, 3 and Days 22, 23, 24) in patients with CF if safety data is acceptable to DSC.

Cohort 5 is included in the study to evaluate for changes in αENaC expression following ARO- ENaC

dosing in NHVs, utilizing samples obtained via bronchoscopy, as there is no known serum marker of pharmacodynamic effect for ARO-ENaC.

CF cohort 6 is included in the study to compare the safety and efficacy of compressing the dosing regimen of ARO-ENaC from daily dosing over three days to one single, larger dose given every two weeks. The rationale for testing this dosing regimen is that sheep pharmacology studies indicate similar efficacy of ARO-ENaC when given via one single, larger dose as when given via three smaller daily doses. Additionally, sheep studies indicate a waning of drug effect at 3 weeks post-dose, providing the rationale for testing a 2 week dosing interval.

All cohorts in the study are double-blind to limit the occurrence of conscious and unconscious bias in trial conduct and interpretation. Blinding will be achieved using a PBO (0.9% normal saline). Inclusion of participants receiving PBO will reduce bias in the assessment of drug safety and tolerability. The patient cohorts are proposed to understand multiple dose safety, pharmacodynamics and pharmacokinetics which should assist with dose selection in later stage clinical studies.

LCI data will be collected for all subjects in cohorts 4b and 6 and for a subset of patients in cohorts 2b and 3b (the subset of patients with ppFEV1 >70%). LCI collection is feasible but time consuming in those with more severe lung disease; for this reason, CF cohorts 2b, 3b and 4b only assess LCI in those with ppFEV1 >70% and CF cohort 4b only enrolls patients with ppFEV1 > 70%. CF cohort 6 trials a different approach, and will collect LCI measurements on all subjects in the cohort, even those with ppFEV1 < 70%.

7.3. DSC and Criteria for Dose-escalation and Dose Limiting Toxicities

Escalation to the next cohort will proceed according to the study design until the highest planned dose cohort is completed, unless the trial is stopped early by the DSC, PI or Sponsor. Dose escalation will require approval by the DSC based on evaluation of all available safety and, when available, pharmacodynamic data through at least Day 21 of the most advanced NHV cohort. The DSC meeting held during CF cohort 4b will review all cumulative safety data to date, through the Day 29 visit of CF cohort 4b.

7.4. Stopping Rules & Data Safety Committee

A decision to stop the trial early or discontinue drug in an individual subject, group of subjects or to halt enrollment temporarily or permanently may be indicated based on any of the following:

1. A single Serious Adverse Event (SAE, defined in Section 11.1) considered at least possibly related to study drug
2. Two cases of a drop from baseline FEV1 (which must be confirmed on repeat within 48 hours) **in healthy volunteer cohorts** of $\geq 20\%$ (absolute decline in % of predicted) considered to be at least possibly related to study drug by study investigator
3. One case of a drop from baseline FEV1 (which must be confirmed on repeat within 48 hours) **in cystic fibrosis cohorts** of $\geq 20\%$ (absolute decline in % of predicted) considered to be probably related to study drug by study investigator.
4. A post-dose increase in serum potassium to > 5.7 milliequivalents/Liter which must be from a non-hemolyzed sample and confirmed by repeat blood draw within 48 hours of initial results.

If any such events occur, within 5 days of Sponsor being notified of the event, the DSC will meet to review the event and determine any necessary actions as detailed below. Further dosing of the subject who triggered the stopping rule will be paused until such DSC review occurs.

Central labs will be utilized. However local labs may be utilized as necessary (including for Screening) if needed by the investigator or for emergent situations, including time critical analytes such as serum potassium and repeat clinical chemistries.

The Sponsor or PI can discontinue any subject at any time with or without DSC consultation. If such events (as described above) occur and the subject is not discontinued from the study the reason for not discontinuing the subject will be included in DSC meeting minutes. Including, but not limited to the events listed above, the DSC may pause the study to additional dosing or dose escalation to provide time to evaluate safety data and recommend the action to be taken, which may include, but is not limited to one of the following:

- Discontinuation of a subject or group of subjects from the study
- The study is stopped immediately with no further dosing
- The study will continue until the current cohort is completed
- The study will continue, but the next dose escalation will be to a level midway between the current level and the next planned level
- The study will continue as planned

The DSC will consist of at least the Sponsor Medical Monitor, Sponsor pharmacovigilance lead, a study Investigator and an independent physician experienced in Phase 1 clinical trials.

7.5. Primary Analysis and Final Analysis

Primary analysis is planned once both all subjects in cohort 6 have completed the Day 43 study visit and all subjects from other cohorts have completed EOS. PIs and study participants will remain blinded through EOS. Sponsor will be unblinded to analyze both safety and efficacy endpoints for all NHV and CF cohorts. Final Analysis is planned when all subjects have ended the study and the database is locked. Safety and efficacy results will be updated based on complete database in final analysis.

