- Determination of urinary excretion and metabolite identification in NHVs (reported in a separate report outside of this study)
- Changes from pre-dose baseline to Day 18 in expression of α ENaC using bronchoscopic brush biopsy samples in NHVs
- Changes from pre-dose baseline to Day 18 in expression of α ENaC using bronchoalveolar lavage (BAL) samples in NHVs
- Changes from pre-dose baseline to Day 18 in cytokine levels as well as cell count and differential in BAL fluid in NHVs

Study Population/Patient Number:

Summary of Participant Profile by Cohort:

- Cohorts 1-4: 6 (randomized 4 active: 2 PBO) NHVs per cohort, adult healthy volunteers
- Cohort 5: 12 adult NHVs (randomized 8 active: 4 PBO); only this cohort will undergo bronchoscopies
- Cohorts 2b, 3b: up to 6 (randomized 4 active: 2 PBO) CF adult patients per cohort
- Cohort 4b: up to 12 (randomized 9 active: 3 PBO) CF adult patients with baseline ppFEV1 of > 70%.
- Cohort 6: up to 24 (randomized 18 active: 6 PBO) CF adult patients

NHV subjects will enroll sequentially into a total of 5 cohorts (with 6 subjects in each of cohorts 1-4 and 12 subjects in cohort 5), randomized to receive ARO-ENaC or PBO (4 active: 2 PBO in cohorts 1-4 and 8 active: 4 PBO in cohort 5) in a double blinded fashion. Dose escalation will occur by Data Safety Committee (DSC) vote after review of cumulative safety once all healthy volunteers in the current cohort have completed their Day 21 study visit. There will be no DSC review during cohort 5. Cohort 5 is added to the study for the purpose of obtaining bronchoscopic samples in NHVs.

CF patient cohorts 2b and 3b will each enroll up to 6 patients to receive escalating multiple doses of ARO-ENaC or PBO. CF patient Cohort 4b will enroll up to 12 patients to receive multiple doses of ARO-ENaC or PBO. CF cohort 6 will enroll up to 24 patients to receive multiple doses of ARO-ENaC or PBO. Cohort 6 is included in the study to assess the safety and efficacy of dosing ARO-ENaC on days 1, 15, and 29 (as opposed to all other CF cohorts which dose on days 1/2/3 and 22/23/24).

CF patients not indicated or not treated with CFTR modulators/correctors at baseline or CF patients on a stable regimen (last 2 months) of CFTR modulators/correctors are eligible. CF patients are required to continue their established treatment regimen for the duration of the study without any changes. Sub-group analysis of CF patients will be conducted according to CFTR modulator/corrector use at baseline.

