6.1. Primary Endpoint

1. The incidence and frequency of adverse events over time through end of study using escalating multiple doses in NHVs and in CF patients.

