7.6. Duration of the Study

For each NHV subject the approximate duration of the study clinic visits is a maximum of 8 weeks from the beginning of the Screening period to the Day 29 End-of-Study (EOS) examination.

For each CF patient, the duration of the study is approximately 20 weeks from the beginning of the Screening period to the Day 113 EOS examination.

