### **7.3 Primary Analysis**

Primary analysis will occur when all subjects in Cohort 6 have completed their Day 43 visit (or have discontinued early) and all other cohorts have completed. EMB and the Sponsor may be unblinded after the data have been entered and cleaned.

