## **9. STATISTICAL METHODS OF ANALYSIS**

For all summary tables and figures described in this SAP, NHV Cohorts 1-5 and CF patient Cohorts 2b-4b and 6 will be summarized separately. Subjects will be grouped by dose and dosing regimen within each table and figure, with subjects receiving placebo pooled across cohorts. All data will be combined in listings, which will be sorted by cohort and subject number.

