#### **9.5.1 Adverse Events**

AEs will be recorded from time of signed consent through to EOS. The PI and clinical facility staff are responsible for detection, recording and reporting of events that meet the criteria and definition of AEs. The investigator will determine the severity and relationship of an AE associated with use of the study drug, and will identify serious adverse events (SAEs). All AE data summaries will report these as recorded on the eCRF.

MedDRA version 23.0 or later will be used to code all events categorized as AEs to a SOC and PT.

An overall summary of AEs will be provided. The overall summary will include the number and percent of subjects experiencing an event as well as the number of events in each of the following

---

categories: AEs, TEAEs, treatment-related TEAEs, SAEs, TESAEs, treatment-related TESAEs, and AEs resulting in study drug withdrawal, study discontinuation, and death. Categories are not mutually exclusive.

Descriptive statistics summaries of subject incidence of AEs will be summarized for all TEAEs, treatment-related TEAEs, TESAEs, treatment-related TESAEs, and AEs resulting in study drug withdrawal or study discontinuation will be tabulated by SOC in alphabetical order and PT in descending order of frequency. Summaries will include count and percent of subjects as well as number of events.

Descriptive statistics summaries of subject incidence of TEAEs by SOC, PT, and relationship to study drug will be provided. Subjects will be counted once under the closest relationship reported within each SOC and PT. Events will be counted the number of times they occur within each SOC and PT.

Descriptive statistics summaries of subject incidence of TEAEs by SOC, PT, and severity will be provided. Subjects will be counted once under the highest severity reported within each SOC and PT. Events will be counted the number of times they occur within each SOC and PT.

All AEs will be listed by subject. Separate by-subject listings of SAEs and of AEs resulting in study drug withdrawal or study discontinuation will be provided.

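### At the primary analysis only, crude adverse-event percentages for Cohort 6 rest on shorter follow-up than those for the lower-dose CF cohorts and pooled CF placebo

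*Protocol*

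**What the plan says.** Protocol 7.5 sets the primary analysis at the point when "all subjects in cohort 6 have completed the Day 43 study visit and all subjects from other cohorts have completed EOS". SAP 7.3 has the same trigger: "Primary analysis will occur when all subjects in Cohort 6 have completed their Day 43 visit". Neither section gives a data cut-off date or a counting window for adverse events.

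Safety is within its scope. Protocol 7.5 states that "Sponsor will be unblinded to analyze both safety and efficacy endpoints for all NHV and CF cohorts". Adverse-event incidence and frequency form the primary endpoint, defined in Protocol 6.1 as "over time through end of study using escalating multiple doses in NHVs and in CF patients". Protocol 7.6 puts a CF patient's participation at "approximately 20 weeks from the beginning of the Screening period to the Day 113 EOS examination".

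Four SAP rules decide what the tables will show:
- Section 5 defines a TEAE as an event on or after the first dose, with no end of window.
- Section 9 groups active subjects by dose and regimen, "with subjects receiving placebo pooled across cohorts".
- Section 9.5.1 uses crude measures: "The overall summary will include the number and percent of subjects experiencing an event", together with the number of events. The tables by organ class and preferred term do the same.
- Section 9.5.8 measures exposure from first to last dose, which is not the time over which adverse events are collected.

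Protocol 7.5 and SAP 7.4 provide for a final analysis on the complete data. SAP 2.2 rules out formal hypothesis testing.

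**The concern.** A crude percentage of subjects with an event rises with the time each subject is watched. At the primary analysis the highest-dose CF cohort is the one watched for the shortest time, while the columns beside it run to Day 113. Even if the drug had no effect on adverse events, Cohort 6 would then tend to show a lower percentage and fewer events per subject than placebo or the lower doses. At stake is how the sponsor, newly unblinded, reads the primary endpoint at the analysis the plan calls primary.

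The SAP already allows for this on the efficacy side. Sections 9.6.1 and 9.6.2 add FEV1 and lung clearance index plots that stop at Day 37 for Cohorts 2b-4b and at Day 43 for Cohort 6. Section 9.5.1 has no counterpart for adverse events.

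**Working it through.** **The plan's own figures.** Table 5 (Protocol 12.1, SAP 3.2) gives the chance of at least one TEAE among n subjects as 1 − (1 − p)^n. For p = 0.3 and n = 4 this is 1 − 0.7^4 = 0.7599, printed as 0.76. All 14 cells reproduce. The table is correct, but it attaches no follow-up time to p.

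**Inputs.**
- Planned CF placebo, from the synopsis: "Cohorts 2b, 3b: up to 6 (randomized 4 active: 2 PBO) CF adult patients per cohort", so 2 + 2; Cohort 4b adds 3 and Cohort 6 adds 6. The total is 13, of whom 2 + 2 + 3 = 7 (54%) are in cohorts that will have reached Day 113. These are planned maxima.
- Cohort 6: 18 active, followed for at least 43 days at the cut.
- Assumed here: p = 0.30 (a value from Table 5) is the incidence by Day 113, with the same constant hazard in every arm. The documents give no accrual figures.

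**Follow-up if everyone in Cohort 6 is cut at Day 43.** Cohort 6 active has 43 days. Pooled placebo has (7 × 113 + 6 × 43)/13 = 1049/13 = 80.7 days on average. The ratio is 80.7/43 = 1.88. With equal event rates, Cohort 6 would show 43/80.7 = 0.53 times as many events per subject as placebo.

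**Incidence.** With t days of follow-up in Cohort 6:
- Cohort 6 = 1 − 0.7^(t/113)
- Pooled placebo = (7 × 0.30 + 6 × Cohort 6)/13
- Lower-dose CF cohorts = 30% by assumption

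For accrual spread evenly over A days, I evaluate at mean follow-up, which is an approximation. For A = 70, t = 43 + 35 = 78. For A = 180, the last 70/180 of patients average 78 days and the other 110/180 have reached 113, so t = (70 × 78 + 110 × 113)/180 = 99.4.

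| Accrual spread | t (days) | Cohort 6 | Pooled placebo | Follow-up ratio |
|---|---|---|---|---|
| none | 43 | 12.7% | 22.0% | 1.88 |
| 70 days | 78 | 21.8% | 26.2% | 1.24 |
| 180 days | 99.4 | 26.9% | 28.6% | 1.07 |

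**Sensitivity, all at a uniform Day 43 cut.**
- Other incidences by Day 113: 20% gives 8.1% v 14.5%; 50% gives 23.2% v 37.6%; 80% gives 45.8% v 64.2%.
- Early clustering, with 80% of the hazard before Day 43: Cohort 6 = 1 − 0.7^0.8 = 24.8%, placebo = (2.1 + 6 × 0.248)/13 = 27.6%.
- True hazard ratio of 1.5 against Cohort 6, constant hazard: 1 − 0.7^(1.5 × 43/113) = 18.4%, still below placebo at 22.0%.

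**Would person-time alone repair it?** Only if the hazard is constant. Take equal hazards with 80% of the cumulative hazard H before Day 43. Cohort 6 then shows 0.8H/43 per day, and placebo (7H + 6 × 0.8H)/1049 = 11.8H/1049. The ratio is 0.01860/0.01125 = 1.65, so Cohort 6 would wrongly look worse.

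**Common window.** With equal hazards and every column counted to Day 43, or every column to Day 113, the expected ratio is 1.00.

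**The case against.** The strongest reply is that the endpoint runs through end of study, so for Cohort 6 it is answered only at the final analysis, where every CF cohort is planned to Day 113. That stands, and it limits the point to the primary analysis. A reader might infer that the trial's final safety results will flatter the highest dose. The documents do not support that.

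Nor does the plan tie a dosing decision to these tables. Cohort 6 is the last cohort, its last dose is on Day 29, and the stopping rules in Protocol 7.4 work on individual events. The tables are descriptive, and SAP 9.5.1 lists all adverse events by subject. A reading that participants are put at risk, or that a formal comparison is biased, goes too far. What remains is possible misreading of an early summary.

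The size is also open to challenge. Day 43 is the minimum, reached exactly only by the last patients in, and a multi-site cohort of 24 will have some spread. SAP 7.3 also waits for data entry and cleaning. A constant hazard is not given by the documents, and events may cluster around dosing. Both points stand, so 12.7% v 22.0% is the boundary under the stated assumptions, not an expected value.

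Finally, the gap is small against chance. One placebo subject is 1/13 = 7.7 points. The standard error of the extreme difference is √(0.127 × 0.873/18 + 0.220 × 0.780/13) = 0.139, about 14 points. That is true, but noise does not cancel a shift of known direction that a date filter removes.

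**Conclusion.** The point holds for the primary analysis and only there. As written, the plan sets crude TEAE percentages and counts for Cohort 6, with 43 to 113 days of planned follow-up, beside columns wholly or mostly followed to Day 113. With equal adverse-event rates this understates Cohort 6 incidence whenever first events arise after the cut. That direction does not depend on the assumed incidence.

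The size does. At 30% by Day 113 and a constant hazard, the shortfall against pooled placebo runs from 9.3 points (uniform Day 43 cut) through 4.4 points (70 days of accrual) to about 1.7 points (180 days). With 80% of the hazard before Day 43 it is 2.8 points even at the uniform cut. Against the lower-dose cohorts, at 30% by assumption, the constant-hazard shortfalls are 17.3, 8.2 and 3.1 points. Accrual, event timing and the 30% are my assumptions. The 7 of 13 is a planned count, which extra patients, replacements or early withdrawals could alter. The change is worth making because it is cheap and concerns the primary endpoint, but the distortion is temporary.

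**What to change.** In SAP 7.3 and 9.5.1, state that for the primary analysis the CF TEAE summaries used to compare cohorts and pooled placebo count events with onset from first dose through Day 43 in every column. Show all later events in a second table or listing, and give the through-EOS tables at the final analysis.

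Events per person-time may be added as a supplement only, because the measure assumes a constant hazard. It needs a derived follow-up time, from first dose to the earlier of the cut and the end of participation; the exposure variable in SAP 9.5.8 will not serve.

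The cost is one SAP rule and a filter on onset dates already collected. There are two small downsides. Late events in the earlier cohorts move to a second table. The window also leaves 43 − 29 = 14 days after the last dose in Cohort 6 against 43 − 24 = 19 days in Cohorts 2b-4b, which a footnote should state. Day 43 is not a scheduled visit in Cohorts 2b-4b, but a filter on onset date does not require one.

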7.6. Duration of the Study

For each NHV subject the approximate duration of the study clinic visits is a maximum of 8 weeks from the beginning of the Screening period to the Day 29 End-of-Study (EOS) examination.

For each CF patient, the duration of the study is approximately 20 weeks from the beginning of the Screening period to the Day 113 EOS examination.

8. PATIENT SELECTION

8.1. Number of Patients

Approximately 36 NHPs and up to 56 CF patients (including up to 2 extra patients per cohort in Screening and not including potential replacements) may be enrolled in the study.

8.2. Inclusion Criteria

Applicable to NHV and CF Cohorts

To be eligible for participation, NHVs and CF patients must meet all the following inclusion criteria:

1. Male or non-pregnant, non-lactating female volunteers 18-55 years of age, inclusive at time of Screening
2. Normal ppFEV1 (>80%) at Screening in NHVs only
3. Able and willing to provide written informed consent prior to the performance of any study specific procedures
4. Participants with a BMI between 18.0 and 35.0 kg/m², inclusive, at Screening
5. A 12-lead ECG at Screening with no abnormalities that may compromise participant's safety in this study
6. Non-smoker (smoker is defined as smoking cigarettes daily for at least the past 12 months) with current non-smoking status confirmed by urine cotinine at Screening AND any previous smoking history prior to 12 months must be < 15 pack years. Patients may be on nicotine replacement (patch or gum). e-cigarettes (vapor) is not permitted. A positive urine cotinine result due to nicotine replacement is acceptable for enrollment at the discretion of the PI.
7. Participants of childbearing potential must agree to use highly-effective contraception during the study and for at least 12 weeks following the end of the study or last dose of study drug, whichever is later. Males must not donate sperm during the study and for at least 12 weeks following the end of the study or last dose of study drug, whichever is later. (See Section 10.6 for details regarding highly-effective contraception).
8. Participants who are willing and able to comply with all study assessments and adhere to the protocol schedule
9. No abnormal finding of clinical relevance at the Screening evaluation other than CF for CF patients
10. No planned significant dietary changes during the study period.

Additional Inclusion Criteria for CF Patients

To be eligible for participation, CF patients must meet all the following inclusion criteria:

1. All other treatments for CF (including CFTR modulators/correctors) have been stable for at least two months (meaning no new medications or changes in dose) prior to first dose and patient is willing to continue this treatment regimen without change for study duration.
2. Confirmed diagnosis of CF based on source verifiable medical record
3. Percent predicted FEV1 of ≥ 40 to $\leq 90\%$ adjusted for age, sex, and height according to NHANES III at the Screening Visit. For Cohort 4b patients must have ppFEV1 $> 70\%$.
4. Participants with a BMI between 18.0 and 35.0 kg/m², inclusive, at Screening. *Participants with BMI between 15-18 kg/m² or between 35-40 kg/m² may be enrolled at the PI's discretion in consultation with Sponsor depending on co-morbidities.*

